9.6 Concomitant Treatment

The clinical study is concerned with two lesions per patient. Within the study no additional concomitant treatment will be offered to the subjects outside the normal local clinical routines. At the recall appointments, normal recall procedures will be applied.

10 Data Management

10.1 Data Management Plan

10.1.1 Data collection

Data collection is done using the CRF that exists in the form of a paper version. The method is to employ paper CRFs to collect the data responses, which are subsequently translated to the monitoring database. These paper CRFs are compiled by the investigator according to the protocol.

10.1.2 CRF tracking

The entries made in the CRF will be monitored by the designated DMG clinical monitor to confirm all requested info and completed CRFs are entered into the database. CRFs are tracked for missing pages and illegible data manually to assure that the data are not lost. In case of missing or illegible data, a clarification is obtained from the investigator and the issue is resolved.

10.1.3 Data validation

Data validation is the process of testing the validity of data in accordance with the protocol specifications. Discrepancy is defined as a data point that fails to pass a validation check. Discrepancy may be due to inconsistent data, missing data, range checks, and deviations from the protocol. Ongoing quality control of data processing is undertaken by the monitor at regular intervals during the course of clinical trial.

10.1.4 Discrepancy management/query resolution

Discrepancy management includes reviewing discrepancies, investigating the reason, and resolving them with documentary proof or declaring them as irresolvable. Discrepancy management helps in cleaning the data and gathers enough evidence for the deviations observed in data. For discrepancies that require clarifications from the investigator, the monitor will discuss the query with the investigator or will be sent to the site. The Investigators will correct the resolution or explain the circumstances that led to the discrepancy in data.

10.2 Data Privacy Protection

Electronic study files will be password protected and reside on a computer that is also password protected. Paper records will be maintained in a locked cabinet in a space that has locked entryways.

10.3 Study Database

Electronic study files as well as paper records, such as CRFs, will be collected and checked for completeness by the clinical monitor during the on-site visits.

A copy of the paper records will be stored at sponsor site. Moreover study data will be transferred into a monitoring specific database.

11 Biostatistical Design

11.1 Prospective Design

Controlled, randomized, double blind study, single center design.

11.2 Determination of Sample Size

Subjects recruited for this investigation will be selected from patients attending the clinical research area and recruited from advertisements (Attached). 150 patients aged 14 years and older will be recruited into the study to provide 150 resin infiltrated and control (no Treatment) lesions. Based on previous studies approximately 20% loss of these subjects will occur over the three year period producing a subject population of 120 who will be available for the 3 year recall.

11.3 Evaluation Strategy

Four trained operators will complete the direct and indirect evaluations of the carious teeth and seal the carious lesions. Two trained and calibrated examiners will complete the evaluation process at each recall. The PI will select all lesions for this study.

11.4 Statistical Analysis

11.4.1 Descriptive Statistics

For the digital subtraction procedure, the ANOVA for Repeated Measures, will be used to determine significance between the two groups ($p=.05$). The remaining endpoints will be listed as percentages rather than subjected to statistical analyses.

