11.4.3 Evaluation of Records

This section was revised and specified in Amendment 1 valid as of 30.11.2015!

The outcome variable will be the caries progression status (regression, no changes or progression) for the selected lesions after 3 years. The radiographs will be read by 2 methods (1) visual independent reading and (2) subtraction radiography of digitized images.

For visual readings the depth of each selected lesion will be visually assessed and recorded by the PI independently on the conventional baseline and follow-up radiographs, respectively. The depth of the selected lesion will be classified into the following scales 1- lesion regressed, 2- lesion expanded, 3 no change in lesion size. A score of 4 (missing surface, generally fractured) and 5 (presence of a restoration) may be assigned when needed. For all visual readings, the examiner will be blinded as to whether the examined radiograph was a radiograph of the lesion was Icon sealed or a control. The examiner will be asked to determine the status (1 to 5) of the right positioned image against the left positioned image of the radiograph.

To assess the progression status on subtraction images the conventional radiographs will be first digitized (Epson Expression 1680 Pro scanner, Photoshop software) in a standard way (TPU format, 8-bit, 3,200 resolution), and contrast and gamma levels will be pre-adjusted pair-wise in the baseline and follow-up images. The images will be stored uncompressed (TIFF 3,650 x 2,425 grayscale) at an individual size of 9–14 Mb. Next, the images will be converted to a readable format for the subtraction software in Adobe Photoshop 6.0 and stored as TIFF 600 x 400 files, with a code corresponding to case number, test/control lesion, baseline or follow-up and involved surface.

The digital subtraction of the digitized images will be undertaken by one of the examiners by means of the Compare software (Dental Health Unit, University of Manchester, UK), which runs as a plug-in to the Image Tool software, version 1.23 [University of Texas Health Science Center at San Antonio,

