Texas, 2002]. The subtraction images will be obtained by subtracting the follow-up from the baseline images of each lesion. First, the two images will be automatically aligned to obtain a relationship with the least difference between them. The difference in density between the two images will then be normalized. Subtraction of images will be conducted, and the contrast stretched. The subtraction images will be coded and randomly organized, as described above, then saved in a Microsoft Powerpoint presentation. For their reading, the subtraction images will be viewed by an external trained examiner 10 days after the visual assessment of conventional radiographs. The presentation will be viewed on a 43.2-cm Hewlett Packard monitor in one session. Additionally, the examiner will be able to access the conventional baseline radiograph to confirm the vertical location of the lesion within the proximal surface. The subtraction progression will be observed as the presence of black points corresponding to an extension of the proximal lesion. Conversely, regression will correspond to the presence of white points and stabilization as an evenly grayish appearance on the image.

Intraexaminer reproducibility will be obtained by rereading 25% of the independent and paired radiographs and of the subtraction images 2 days after the first reading.

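### The protocol assigns repeated-measures ANOVA to a subtraction reading that, as printed, has three categories and no numeric score, while the SAP tests radiographic change by McNemar and omits subtraction

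*Combined protocol and SAP*

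**What the plan says.** **Protocol, test.** Section 11.4.1: "For the digital subtraction procedure, the ANOVA for Repeated Measures, will be used to determine significance between the two groups", at the 0.05 level. The next sentence removes every other endpoint from testing: "The remaining endpoints will be listed as percentages rather than subjected to statistical analyses".

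**Protocol, outcome.** Section 11.4.3: "The outcome variable will be the caries progression status (regression, no changes or progression) for the selected lesions after 3 years". Films are read in two ways.

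- Subtraction images are read by eye. "The subtraction progression will be observed as the presence of black points corresponding to an extension of the proximal lesion", whereas "regression will correspond to the presence of white points and stabilization as an evenly grayish appearance on the image". No score, unit or measured quantity is attached.
- Conventional films are read visually: "For visual readings the depth of each selected lesion will be visually assessed and recorded by the PI independently". This reading carries the codes "1- lesion regressed, 2- lesion expanded, 3 no change in lesion size". In addition, "A score of 4 (missing surface, generally fractured) and 5 (presence of a restoration) may be assigned when needed".

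**Protocol, status.** Section 6.2 lists change in lesion size as Specific Aim II, under the primary endpoints.

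**SAP, Statistical Analysis.** Radiographic change is a secondary outcome, defined as movement to the next depth category on pairwise comparison of films and tested with McNemar's test and a 95% CI. Repeated-measures ANOVA appears only for a subgroup analysis by caries risk. Subtraction is not mentioned.

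**The concern.** A repeated-measures ANOVA compares means, so each lesion needs a number. The printed reading rule gives each lesion a category. Before the test can be run, someone must choose a score, and the protocol does not say which. The only inferential test the protocol offers for one of its two primary aims is therefore not fully pre-specified.

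The SAP does not close the gap. It uses a different test on a different reading, gives that outcome a different rank, and does not say what happens to subtraction. With two readings and two tests for one aim, and neither named as deciding, the choice could be made after the results are seen.

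There is also a trap. The only numeric codes in section 11.4.3 put expansion, the worst of the three states, between regression and no change. They suit data entry but not averaging. An analyst looking for numbers to feed the ANOVA would find no others.

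**Working it through.** **1. The plan's own figure.** The SAP gives 23 pairs for 68% vs 30% without progression, a difference of 37.8 points, alpha 0.05 and power 80%. It states no within-pair SD or correlation.

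- Discordant share under independence = 0.68 × 0.70 + 0.32 × 0.30 = 0.572.
- SD of the paired difference = √(0.572 − 0.38²) = 0.654.
- n = ((1.96 + 0.842) × 0.654 / 0.378)² ≈ 23.5, so 24 pairs. The t-based version gives 26 at correlation 0 and 23 to 24 at correlation 0.1.

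The figure reproduces closely. It was built on a within-pair difference of proportions in a binary outcome, not on a mean score.

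**2. The documents side by side.**

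| | Protocol 11.4.1 and 11.4.3 | SAP |
|---|---|---|
| Reading tested | Subtraction images | Pairwise comparison of radiographs |
| Form of the result | Progression, regression or stable | Moved to next depth category |
| Test | Repeated-measures ANOVA | McNemar |
| Rank | Primary (Aim II, section 6.2) | Secondary |

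**3. What happens if the visual codes are used as scores.** This is conditional; section 11.4.1 does not prescribe it.

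Inputs: 3-year progression of 32% (infiltrated) vs 70% (control), from section 4.3.4; 150 × 0.80 = 120 pairs, from section 11.2. Assumptions: independence within pairs, no regression in controls, two-sided 0.05, one comparison at 3 years (a two-level repeated-measures ANOVA, equal to a paired t-test).

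With p the share progressed and r the share regressed, the arm mean is

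1·r + 2·p + 3·(1 − r − p) = 3 − 2r − p.

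The contrast, Icon minus control, is therefore

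(p_control − p_Icon) − 2 × (r_Icon − r_control) = 0.38 − 2 × (excess regression on Icon).

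It is zero when the excess is 0.38 / 2 = 0.19.

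| Regression on Icon (assumed) | Mean, Icon vs control | Difference | Power, printed codes |
|---|---|---|---|
| 0% | 2.68 vs 2.30 | +0.38 | about 100% |
| 5% | 2.58 vs 2.30 | +0.28 | 98% |
| 10% | 2.48 vs 2.30 | +0.18 | 67% |
| 15% | 2.38 vs 2.30 | +0.08 | 19% |
| 19% | 2.30 vs 2.30 | 0.00 | about 5% (both directions) |

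Powers are from 20,000 simulated trials. Hand check at 10%: the variances are 0.4496 (Icon) and 0.2100 (control), so SE = √(0.6596 / 120) = 0.0741 and 0.18 / 0.0741 = 2.43. Against a critical value of 1.98 this gives power of about 67%.

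**4. The same scenarios scored sensibly.** Exact McNemar on progressed yes/no has about 100% power in every row. So does the ANOVA if the categories are scored in order (regressed, no change, expanded). With 10% regression in both arms, even the printed codes keep 99.6% power in the right direction.

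**The case against.** The strongest reply is that the codes are printed for the visual reading, while section 11.4.1 confines the ANOVA to subtraction and leaves every other endpoint untested. Taken literally, the protocol never averages those codes. That is correct, and the power figures above describe a possible misuse, not the stated plan.

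A reader might infer from the code order that the Aim II test will hide or reverse a real effect. The documents do not support this. It requires the visual codes to be carried into the subtraction analysis, and then an excess of regression on Icon of about 19 points for cancellation or more for reversal. No regression rates are given. With none, or equal rates in both arms, direction and nearly all power are kept. Nor would the result depend on regression alone; the contrast contains both the progression and the regression difference.

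ANOVA on categories is also not disastrous in itself. With ordered or 0/1 scores it decides much as McNemar does here. The defect is the undefined score.

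A reader might also suppose that repeated measures means losing every patient who misses an annual film. Section 11.4.1 names no time factor and section 11.4.3 sets the outcome at 3 years, so this cannot be concluded.

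Finally, it would go too far to say that subtraction can only ever give three categories. Section 8.1 speaks of differences in lesion extent and density, and sections 8.1 and 11.4.3 are marked as revised by Amendment 1, whose text is not visible. A continuous measure may be defined there.

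What remains is that the printed test and the printed outcome do not fit each other, and that protocol and SAP disagree.

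**Conclusion.** The point holds as a specification gap and a conflict between documents. The protocol's only inferential test has no defined numeric input in the text available, and the SAP uses another test on another reading for the same aim.

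The mismatch alone has no calculable effect on the result, because no subtraction score is defined. If the visual codes were averaged, power at 120 pairs and 32% vs 70% progression would be about 100%, 67% and 5% for an excess of regression on Icon of 0, 10 and 19 points. This rests on independence within pairs, no regression in controls, a single 3-year comparison and assumed regression rates.

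This is a correction to settle before analysis. It is not evidence that the trial's conclusion is in danger, and confidence is limited by the unseen amendment text.

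**What to change.** 1. In section 11.4.1, replace the ANOVA with McNemar's exact test on progressed yes/no at 3 years within patient, and report the paired risk difference with its 95% CI. This matches the SAP's test for radiographic change.
2. Name either subtraction or the visual pairwise reading as the deciding one and the other as a sensitivity analysis. Define progressed for each, and use the same choice in both documents.
3. State the rank of radiographic change, primary or secondary, identically in protocol and SAP.
4. State in section 11.4.3 that the visual codes 1 to 5 are labels and are not to be averaged.
5. If subtraction does yield a continuous measure of extent or density, define the variable and its unit, cite where it is specified, and use a paired or mixed model in place of item 1.

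An ordinal or logistic model clustered on patient could be added as support but is not needed. The cost is wording in protocol and SAP. Items 1 to 4 need no new data.

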4.2.1 Hypothesis I

Infiltrated early caries lesions in a high caries risk population have a lower incidence of lesion progression when compared to lesions managed by regular preventive regimen. The number of lesions requiring an invasive intervention (filling) is significantly lower than for lesions treated with standard regimens.

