4.2.2 Hypothesis II

Infiltrated early caries lesions in a high caries risk population have a lower rate of lesion progression when compared to lesions managed by regular preventive regimens.

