6.1 Objectives

The main purpose of the present study is to evaluate the efficacy of the Icon Caries Infiltration system, DMG, Hamburg, Germany) in controlling the progression of non-cavitated proximal lesions in posterior teeth.

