6.2 Specific Aimes (Primary Endpoints)

6.2.1 Specific Aim I

Significant lower rate of invasive interventions (filling) compared to standard treatment

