6.2.2 Specific Aim II

Change in lesion size (Radiographic analyses)

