6.4 Study Overview

To confirm or reject the hypotheses a prospective, double-blind, randomized controlled trial (RCT) is designed to investigate the clinical performance of resin-infiltration as early caries management in a caries-prone population.

This CIP describes a three-year longitudinal, prospective, randomized controlled trial in split mouth design. The study includes a clinical team involving one on-site Principal Investigator (Site-PI)/operator and one back-up Clinical Investigator (CI)/operator.

The clinical site will enroll 150 subjects (in the age range of 14 years or older) with 2 study lesions. If the lesion management provided in the study appears to be insufficient within the investigated period, the study will provide a maximum of 2 traditional restorations for free to participants. The patients will be evaluated at six time points over a period of 3 years. Lesion status and caries risk will be monitored at 6-month intervals, while radiographic evaluation will be conducted at 12-month intervals at 1-, 2- and 3-year recall visits.

7 Design of the Clinical Investigation

The study will be designed as a controlled, double blind, randomized, prospective trial with a three year follow-up period regarding to CONSORT²² recommendations as a single-center study to investigate the effect of caries infiltration as an alternative treatment option.

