A previous infiltration study by Martignon et al. [5] reported a 3-year difference of proportions of 37.8% (95%CI: 20.5-55.2%) with (resin infiltration (68%) vs. control (30%)). Based on this and with alfa = 0.05 and a power of 80% the calculated sample size (t-test; matched pairs) would be 23 lesion pairs (thus 23 participants) to find significant differences. However, this study aimed to enroll 150 participants to not only allow for a potentially high attrition rate (20%) over a period of 3 years, but also aiming to better quantify the efficiency of the treatment effect.

Statistical Analysis

All evaluations are performed by two trained and calibrated examiners. The primary outcome is proportion of lesions that required restorative treatment (filling) after 3 years as measured via dental examination. Differences between groups will be tested using Fisher's exact test and ANOVA for Repeated Measures for subgroup analysis based on caries risk. Secondary outcomes are change in categorical lesion depth (progression to next depth category lesion; E1->E2->D1->D2->filling) after 6 months and 1, 2 and 3 years as measured by pairwise comparison of radiographs as well as the influence of Icon treatment on clinical parameters. Differences will be analyzed with McNemar's test with 95% confidence interval (95% CI) and P = .05.

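### The protocol leaves fillings, a primary endpoint, without a test, while the SAP makes them the primary outcome and appears to test them with Fisher's exact test, which ignores the split-mouth pairing

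*Combined protocol and SAP*

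**What the plan says.** **Protocol, endpoints and hypotheses.** Section 6.2, whose heading calls the aims primary endpoints, lists two. Aim I reads "Significant lower rate of invasive interventions (filling) compared to standard treatment". Aim II is radiographic change in lesion size. The second sentence of Hypothesis I (4.2.1) makes the same claim about fillings: "The number of lesions requiring an invasive intervention (filling) is significantly lower than for lesions treated with standard regimens". The first sentence of Hypothesis I, and Hypothesis II (4.2.2), concern progression.

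**Protocol, analysis.** Section 11.4.1 names one test, repeated-measures ANOVA on the digital subtraction result. It continues: "The remaining endpoints will be listed as percentages rather than subjected to statistical analyses". Section 11.4.3 describes the outcome variable as progression status at 3 years.

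**SAP, Statistical Analysis.** "The primary outcome is proportion of lesions that required restorative treatment (filling) after 3 years". The next sentence names Fisher's exact test for group differences, together with repeated-measures ANOVA for caries-risk subgroups. Categorical lesion depth and clinical parameters follow as secondary outcomes, and McNemar's test comes after them.

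**Design.** Section 6.4 describes a "randomized controlled trial in split mouth design". Under 9.3 each patient has one Icon tooth and one placebo tooth.

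**The concern.** Three things do not fit together.

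- The protocol claims significance for fillings and then excludes them from testing.
- The SAP makes that untested endpoint the primary outcome and moves lesion change, primary in 6.2, to secondary. Yet the main purpose in 6.1 is "controlling the progression of non-cavitated proximal lesions in posterior teeth".
- The test that the SAP appears to attach to fillings is for two independent groups, although every patient supplies both lesions.

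With two incompatible plans and no visible rule on which prevails, the primary analysis could be settled after results are known. If Fisher's test is used and a patient's two lesions tend to share the same fate, a real difference is more likely to be missed.

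**Working it through.** **1. The test for each claim**

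| Claim | Protocol 11.4.1 | SAP, by sentence order |
|---|---|---|
| Fillings (Aim I; Hypothesis I, second sentence) | none, percentages only | primary; Fisher's exact |
| Lesion change (Aim II; Hypothesis I, first sentence; Hypothesis II) | repeated-measures ANOVA on subtraction | secondary; McNemar |

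The protocol has no test of fillings. It does have one for progression.

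**2. What the sample size covers.** The SAP uses 68% vs 30%, a difference of 37.8 points, alpha 0.05, power 80% and a matched-pairs t-test, and obtains 23 pairs. With SD of the paired difference = √(p₁q₁ + p₂q₂ − 2ρ√(p₁q₁p₂q₂)):

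- ρ = 0: SD = √(0.2176 + 0.2100) = 0.654; n = ((1.960 + 0.842) × 0.654 / 0.378)² = 23.5, so 24.
- ρ = 0.05: SD = 0.637; n = 22.3, so 23.

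The stated figure is therefore reproduced under a small assumed correlation. But 68 = 100 − 32 and 30 = 100 − 70, and 32% vs 70% are the three-year radiographic progression rates quoted in protocol 4.3.4. The calculation sizes progression. Neither document gives a filling rate.

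**3. Power for fillings.** Evaluable pairs: 150 × 0.8 = 120 (protocol 11.2). Filling rates, correlations and a two-sided 0.05 level are assumptions.

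With control rate c, Icon rate t and correlation ρ, the proportion of pairs with both filled is p₁₁ = ct + ρ√(c(1−c)t(1−t)). Control only is c − p₁₁ and Icon only is t − p₁₁. For 15% vs 5% and ρ = 0.3:

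- p₁₁ = 0.0075 + 0.3 × 0.0778 = 0.0308
- control only 0.1192, Icon only 0.0192

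Exact McNemar uses only the discordant pairs. Fisher uses the two totals as if they came from 240 unrelated lesions. Power, McNemar / Fisher:

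| Assumed filled, control vs Icon | ρ = 0 | ρ = 0.3 | McNemar significant, Fisher not (ρ = 0.3) |
|---|---|---|---|
| 5% vs 2% | 14 / 13% | 15 / 9% | 6% of trials |
| 10% vs 5% | 23 / 22% | 31 / 18% | 13% |
| 15% vs 5% | 68 / 67% | 83 / 70% | 13% |
| 20% vs 5% | 93 / 93% | 99 / 97% | 2% |

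At ρ = 0 the last column would be at most 1.6%.

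**4. False-positive rate.** With equal rates of 5% to 20%, both tests reject in about 2% to 3% of trials at ρ = 0. At ρ = 0.3 McNemar stays at about 2% to 3% and Fisher falls to about 1%.

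**5. Illustration.** Of 120 pairs, suppose 4 have both lesions filled, 14 the control only, 4 the Icon only and 98 neither. Totals are 18 vs 8.

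- Correlation: (4 × 98 − 14 × 4) / √(18 × 102 × 8 × 112) = 0.26.
- Fisher on 18/120 vs 8/120: p = 0.060.
- Exact McNemar: 2 × P(X ≤ 4 | 18, 0.5) = 2 × 4048 / 262144 = 0.031.

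**The case against.** **The Fisher reading is not certain.** The subgroup phrase in the SAP can be taken to cover both Fisher's test and the ANOVA. The McNemar sentence is not expressly limited to secondary outcomes, and it alone in that section carries a significance level and confidence interval. On that reading fillings may already have a paired test. This stands as a limit on the Fisher part. It does not rescue the plan: the primary test is then ambiguous, and 11.4.1 still rules out any test.

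**Fillings partly enter the McNemar analysis.** The SAP's depth scale ends in a filling, and Table 14.2 scores lesions filled after deep progression as progressed. This softens the practical loss but gives fillings no test of their own.

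**The SAP may be the later text.** Amendments 1 and 2 are listed but not shown, so alignment elsewhere cannot be excluded. However, the Amendment 1 revision note appears at 8.1 and 11.4.3 and not at 11.4.1, and no visible text says that the SAP prevails.

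**The size is assumed.** At zero correlation the two tests practically agree, and the illustration was chosen to straddle 0.05. Because Fisher's error is conservative, a significant Fisher result would not be undermined. This is correct, and it limits the seriousness.

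**Exact McNemar is itself conservative.** An asymptotic version would also respect the pairing. What matters is that one paired test is named in advance.

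**Conclusion.** The concern holds. The conflict over whether fillings are tested, and over whether lesion change is primary, follows from the text alone and needs no assumption. The mismatch between Fisher's test and the design rests on the natural, though not the only, reading of the SAP. Its cost is power, with no inflation of false positives. Over the assumed rates at 120 pairs the loss is about 2 to 13 percentage points at correlation 0.3 and practically nil at correlation 0. The true loss cannot be stated, because the documents give neither filling rates nor a within-patient correlation. The point should be corrected, but it would not invalidate a positive result.

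**What to change.** 1. **One paired test for fillings.** Exempt fillings from the percentages-only rule in 11.4.1. In both documents name exact McNemar at two-sided 0.05 in place of Fisher's test, fixed before unblinding. If fillings by treatment have already been seen, label the change post hoc and report both p-values. Limit the SAP's ANOVA sentence expressly to the caries-risk subgroups.
2. **Define the endpoint.** State whether a tooth treated for pulpitis, which Table 14.2 scores as progressed and failed, counts as filled. State also how a lesion treated by an outside dentist is counted, since Table 14.2 scores that patient as a drop-out and the pair would leave the comparison.
3. **One hierarchy.** Reconcile 6.2, 11.4.3 and the SAP: either fillings as the single primary with lesion change secondary, or both primary with a stated alpha split such as 0.025 each. The choice is the sponsor's.
4. **Sample size.** State in the SAP that the 23 pairs refer to radiographic progression, and that power for fillings depends on rates not given.
5. **Amendments.** Check 11.4.1 and 11.4.3 against Amendments 1 and 2 before altering the subtraction ANOVA. If the subtraction reading is still categorical, compare progressed vs not progressed by McNemar.

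**Cost.** Text amendments only, with no new data or visits. Making lesion change secondary takes primary status from the outcome that matches 6.1 and is the only one with a documented effect size. Splitting alpha lowers McNemar power for fillings (assumed 15% vs 5%) from 68% to 57% at correlation 0, and from 83% to 75% at 0.3. Power for progression at 70% vs 32% stays above 99.9%.
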